2.6.3. BASED ON CENTRALIZED ASSESSMENTS. ITT

The tables below will record the **response at 6 and 12 weeks**, based on **centralized assessments** TAC. As for the local evaluations. The centralized evaluations will be reviewed following the criteria specified in the protocol for the evaluation of the main endpoint:

"Patients who are alive and without evidence of progression at this time will be considered as successes, and those who have progressed or died at this time will be considered as treatment failures. Patients in whom it is unknown whether or not there is progression will also be considered as failures. "

In the **ITT population**, both 6 and 12 weeks.

Table 44. Response to treatment: Value. Centralized at 6 and 12 weeks ITT

		Cohort A	Cohort B	Total	p-value
		N (% , 95% CI)	N (% , 95% CI)	N (% , 95% CI)	
Response at 6 weeks	PD				
	SD				
	PR				
	Total				
Response at 12 weeks	PD				
	SD				
	PR				
	Total				

1: Chi-square; 2: Fisher's exact test

Responses will be recoded according to **clinical benefit (CR, RP or EE)** and in the ITT population.

Table 45. Clinical benefit, response to treatment: Value. centralized at 6 and 12 weeks ITT

		Cohort A	Cohort B	Total	p-value
		N (% , 95% CI)	N (% , 95% CI)	N (% , 95% CI)	
Response at 6 weeks	Yes				
	No (PD)				
	Total				
Response at 12 weeks	Yes				
	No (PD)				
	Total				

1: Chi-square; 2: Fisher's exact test

GEIS-30 STUDY

Statistical analysis plan

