## **5. STUDY DESIGN**

### **5.1. Development Phase**

A two cohort Phase II, open-label, non-randomized, multi-center study with 5 centres in Spain and 5 centres in Germany to evaluate the activity and tolerability of Pazopanib in patients with advanced and/or metastatic liposarcoma who have relapsed following standard therapies or for whom no standard therapy exists.

The drug will be separately investigated in the following liposarcoma subtypes (cohorts):

- Well-differentiated liposarcoma/de-differentiated liposarcoma (ALT-WD)
- Myxoid/round cell liposarcoma.

A total of 17 eligible and treated patients will be included (in each stratum) in the first step of the study. If  $\leq 3$  successes are observed in a stratum, the trial will be stopped in this stratum with the conclusion that the drug should not be further investigated in this histology. Otherwise, patients will continue to be accrued. Each cohort will independently recruit a maximum of 37 patients. The statistical analysis will be performed in each stratum.

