### **10.2. Efficacy assessment**

Disease should be captured and target/non-target identified at baseline by CT or MRI as appropriate. Subsequently, imaging studies required to investigate known disease should be performed on week 6/7, on week 12 and every 8 weeks thereafter. Imaging methods will be employed consistently during the course of each patient's evaluation during the study. After discontinuation of protocol treatment, patients who have not progressed will still be re-evaluated every 8 weeks, unless they have started a new anti-cancer therapy, withdrawal of consent or death, whichever occur first. 10.2.1. Efficacy assessment populations:

Intent to treat (ITT) analysis: Efficacy analysis will be carried out in the ITT population. All patients participating in the study will be included in the analysis of efficacy.

Per Protocol (PP) analysis: Efficacy analysis will be carried out in per protocol population. All patients participating in the study and received at least 3 weeks of treatment with Pazopanib with no major protocol deviations will be included in the analysis of efficacy.

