1.10. DESIGN

Phase II study of two cohorts, open, non-randomized and multicenter with 11 participating centers in Spain and 5 in Germany. To evaluate the activity and tolerability of pazopanib in patients with advanced and / or metastatic liposarcoma who have relapsed after standard treatment or for whom there is no established treatment.

The drug will be investigated separately in the following liposarcoma subtypes (cohorts):

- Well-differentiated liposarcoma / dedifferentiated liposarcoma (ALT-WD)
- Myxoid liposarcoma / round cell liposarcoma.

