2.3. ITT and PP POPULATIONS

To determine ITT and PP populations, the definitions specified in the protocol will be followed:

- Analysis by Intention to Treat (**ITT**): Efficacy analyses will be calculated on the population by intention to treat. All patients participating in the study will be included in the efficacy analysis.
- Analysis by Protocol (**PP**): Efficacy analyses will be calculated on the protocol population. All patients participating in the study and who have received at least 3 weeks of treatment with Pazopanib (without major protocol deviations) will be included in the efficacy analysis.

Table 36. ITT and PP Populations

		Cohort A	Cohort B	Total	p-value
		N (%)	N (%)	N (%)	
ITT population	Yes				
	Total				
Duration tt Pazopanib (weeks)	<3 weeks				
	≥3 weeks				
	Ongoing (no end date of tt)				
Total					
Population PP	No				
	Yes				
	Total				

1: Chi-square; 2: Test Fisherexact

Pacientes with less than 3 week of pazopanib treatment:

Table 37. Patients with duration of pazopanib <3 weeks

Study Subject ID	Cohort	PP population	Reason excluded from PP population	Tx Pazopanib duration (days)

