2.6. EFFICACY: MAIN ENDPOINT

Following the instructions of the protocol primary efficacy endpoints in populations ITT and PP will be calculated following the criteria:

Patients who are alive and without evidence of progression at this time will be considered successes, and those who have progressed or died at this time will be considered treatment failures. Patients in whom progression is unknown or not available will also be considered failures. Diagnosis of progression should be based on measurements of tumor lesions, according to the RECIST 1.1 criteria.

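### The p-value planned beside the primary endpoint in SAP 2.6 compares the two cohorts; the protocol's per-stratum two-stage test against 20% is not carried into that section

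*SAP*

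**What the plan says.** Protocol 10.4 applies a Simon optimal two-stage design separately in each stratum. The null rate is 20%, the alternative 40%, and the type I and type II errors are 10% each. A stratum stops if 3 or fewer of its first 17 eligible and treated patients succeed, and is positive if 11 or more of 37 do. Protocol 5.1 adds: "The statistical analysis will be performed in each stratum". SAP 1.10 agrees: "The drug will be investigated separately in the following liposarcoma subtypes (cohorts").

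SAP 2.6 opens with "Following the instructions of the protocol primary efficacy endpoints in populations ITT and PP will be calculated following the criteria" and then gives the success/failure classification. Tables 40 to 47 follow. Each has columns for Cohort A, Cohort B, Total and a p-value, with the footnote "1: Chi-square; 2: Fisher" (exact test). The week-12 row of "Table 45. Clinical benefit, response to treatment: Value. centralized at 6 and 12 weeks ITT" is the protocol's primary endpoint. It shows N, percentage and 95% CI per cohort.

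The populations tabulated are ITT and PP. For ITT, SAP 2.3 says "All patients participating in the study will be included in the efficacy analysis", matching Protocol 10.2: "All patients participating in the study will be included in the analysis of efficacy".

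**The concern.** Section 2.6 claims to follow the protocol but takes over only the definition of success. It does not mention the 20% reference, the first 17 patients, the cut-off of 11, the 10% error rate or any one-sample test. The p-value it does plan tests whether the two histologies differ, which is not a protocol hypothesis.

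A reader of the primary table would see one p-value and could take it as the test of the primary endpoint. A non-significant result would say nothing about whether either cohort beat 20%. A significant one would show a difference without showing which cohort, if any, passed.

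There is also a gap in the analysis set. The rule in Protocol 10.4 applies to eligible and treated patients. Section 2.6 tabulates ITT and PP only, and does not say which set feeds the decision.

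**Working it through.** **Inputs.** From Protocol 10.4: p0 = 0.20, p1 = 0.40, n1 = 17, stop at ≤ 3, n = 37, positive at ≥ 11. SAP 2.6 states no significance level for the cohort comparison, so a two-sided 0.05 is assumed, with 0.10 as a check.

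**Reproducing the design.** With X1 ~ Bin(17, p) and X2 ~ Bin(20, p),

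P(positive | p) = Σ over x = 4…17 of P(X1 = x) · P(X2 ≥ 11 − x).

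- p = 0.20: 0.0948, the exact type I error. The probability of stopping at stage 1 is 0.549.
- p = 0.40: 0.9033, the exact power.

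The protocol's design reproduces.

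**The test that section 2.6 leaves out.** The two-stage p-value for s successes in 37 is P(X1 ≥ 4 and X1 + X2 ≥ s | 0.20). The one-sided 90% lower bound is the p at which that probability equals 0.10. The 95% CI is Clopper-Pearson.

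| s of 37 | Two-stage p | 90% lower bound | 95% CI |
|---|---|---|---|
| 11 | 0.0948 | 20.2% | 15.9–47.0% |
| 12 | 0.0488 | 22.4% | 18.0–49.8% |
| 13 | 0.0223 | | 20.2–52.5% |
| 14 | 0.0091 | | |

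**What the A-versus-B test shows instead.**

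- 15/37 v 15/37 (both positive): Fisher p = 1.0.
- 7/37 v 7/37 (both negative): Fisher p = 1.0.
- 14/37 (positive, two-stage p 0.009) v 3/17 (stopped): Fisher p = 0.21.
- Against 3/17, Fisher first reaches 0.05 at 18/37 (p = 0.038). The protocol's positive zone starts at 11/37.

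**Over repeated trials.** Both cohorts were enumerated under the two-stage rule, with a stopped cohort held at 17. The decision probabilities follow from the two figures above:

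- both positive at 40/40: 0.9033² = 0.816;
- both negative at 20/20: (1 − 0.0948)² = 0.819;
- decisions differ at 40/20: 0.9033 × 0.9052 + 0.0967 × 0.0948 = 0.827.

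| True rates | Protocol outcome | Fisher ≤ 0.05 | Chi-square ≤ 0.05 (uncorrected) | Fisher ≤ 0.10 |
|---|---|---|---|---|
| 40/40 | both positive 81.6% | 4.2% | 6.7% | 8.7% |
| 20/20 | both negative 81.9% | 2.6% | 2.8% | 4.3% |
| 40/20 | decisions differ 82.7% | 32.0% | 40.5% | 45.2% |

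With both cohorts fixed at 37 and no stopping, the Fisher figures at 0.05 are 2.7%, 2.6% and 38%; chi-square gives 4.7%, 5.0% and 47%.

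**Whether the planned 95% CI can stand in for the test.** At 11 and 12 of 37 the rule is met, but the interval includes 20%. A final total of 11 or 12 occurs in 0.0948 − 0.0223 = 7.2% of cohorts at a true 20%, and in 13.5% at a true 40%. Requiring the lower limit to exceed 20% would need 13/37, which changes the type I error to 0.022 and the power to 0.769.

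**The case against.** Five points can be made for the plan.

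- **Parts of the SAP are not visible.** The text jumps from the inclusion criteria to Table 5, and a methods section could lie between. This stands as a limit: the finding covers section 2.6, which can be read in full, and does not claim that the whole SAP lacks the test.
- **The protocol rule is a count rule and still governs.** It needs no p-value, and the final count can be read from the Yes row of Table 45. It is true that no go/no-go decision changes. But no table in 2.6 shows the count in the first 17, the decision itself or the eligible and treated set, and the one p-value shown tests something else.
- **The A-versus-B column is a template feature.** The same layout serves vital signs, laboratory values and adverse events, and no sentence calls it the primary test. That it compares cohorts is read from the layout and footnote. This explains how the column arose, but it remains the only inference beside the primary result.
- **The percentages depend on assumptions.** The 0.05 level and the fixed 17 for a stopped cohort are both assumed. Changing either moves the figures without altering the conclusion.
- **ITT and PP come from the protocol.** That is correct, so the mismatch with the eligible and treated set starts there. It is probably small, since eligibility deviations are not allowed and central pathology review precedes entry. Section 2.6 should still name the set used for the decision.

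**Conclusion.** The concern holds for SAP 2.6. The planned p-value tests a difference between histologies that the protocol never poses, and the section omits the one-sample test against 20% on which each stratum is to be judged. At true rates of 40% and 20% the stratum decisions differ in 82.7% of trials, while the printed test reaches 0.05 in 32.0% (Fisher) or 40.5% (chi-square), and Fisher reaches 0.10 in 45.2%. When the cohorts share a rate, the test cannot tell both active from both inactive. The 95% CIs do not fill the gap, because they conflict with the rule at 11 and 12 of 37.

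This is an error of planned inference and reporting that should be fixed; the decision rule itself is unchanged. The two-stage figures model the Simon rule alone. They assume that the additional sequential and futility procedure in Protocol 10.4 acts only to stop a stratum.

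**What to change.** In SAP 2.6, for week-12 success by central review, report for each cohort:

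1. Successes in the first 17 and in the 37 patients, with the decision against ≥ 4/17 and ≥ 11/37.
2. The two-stage one-sided p-value against 20% and the matching one-sided 90% lower bound (0.095 and 20.2% at 11/37).

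Apply the rule to the eligible and treated patients in order of inclusion, because Protocol 10.4 lets accrual continue during the stage 1 analysis. Show the ITT result alongside.

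If a stratum stops at stage 1, report x/17 with P(X ≥ x | 17, 0.20); for 3/17 this is 17.6% and p = 0.69. Treat any extra patients as descriptive. If fewer than 37 are attained, keep the protocol cut-off and give the exact two-stage p-value at that n (11 successes: 0.082 at n = 36, 0.070 at n = 35), without setting a new rule. State the assumption about the sequential and futility procedure.

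Remove the A-versus-B p-value from the primary table or label it descriptive, and label the 95% CI descriptive. Rename the No (PD) row so that it also covers death and unknown status, since the rule above Table 44 says "Patients in whom it is unknown whether or not there is progression will also be considered as failures".

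The cost is SAP wording and light programming, with no new data or patients and no change to the protocol's decision rule.

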2.6.4. EFFICACY BASED ON CENTRALIZED ASSESSMENTS. PP

Table 46. Response to treatment: Centralized evaluations at 6 and 12 weeks PP

		Cohort A	Cohort B	Total	p-value
		N (% , 95% CI)	N (% , 95% CI)	N (% , 95% CI)	
Response at 6 weeks	PD				
	SD				
	PR				
	Total				
Response at 12 weeks	PD				
	SD				
	PR				
	Total				

1: Chi-square; 2: Fisher's exact test

Responses will be recoded according to **clinical benefit (CR, RP or EE)** and in the PP population.

Table 47. Clinical benefit, response to treatment: Centralized evaluations at 6 and 12 weeks PP

		Cohort A	Cohort B	Total	p-value
		N (% , 95% CI)	N (% , 95% CI)	N (% , 95% CI)	
Response at 6 weeks CLINICAL BENEFIT	Yes				
	No (PD)				
	Total				
Response at 12 weeks CLINICAL BENEFIT	Yes				
	No (PD)				
	Total				

1: Chi-square; 2: Fisher's exact test

GEIS-30 STUDY

Statistical analysis plan

2.7. EFFICACY: SECONDARY ENDPOINT PROGRESSION FREE SURVIVAL (PFS)

2.7.1. PFS. LOCAL ASSESSMENT. ITT

Table 48. Progression-free survival at 12 and 24 weeks according to cohorts (local assessment. ITT)

Progression-free survival	N events	N patients at risk	% Estimated cumulative survival ratio	95% CI		
at 12 weeks	Cohort A					
	Cohort B					
at 24 weeks	Cohort A					
	Cohort B					
Progression-free survival	Strategy	N (%) events	Median (weeks) Min-Max	Standard error	95% CI	p-value ¹
Progression-free survival	A					
	B					
	Total					

1: Log-rank test

Figure 1. Progression-free survival according to cohorts (Local assessment ITT). Kaplan-Meier curve.

Table 49. Progression during follow-up (local assessment. ITT)

Progression-free survival	Cohort A	Cohort B	Total	p-value
PD				
Alive: Free of progression				
Total				

1: Pearson Chi-square; 2: Fisher's exact test

Table 50. Types of progressions / censorship during follow-up (local assessment. ITT)

Progression-free survival	Cohort A	Cohort B	Total	p-value
Progression-Disease progression Clinical progression				
Alive without PD at the end of follow-up				
Alive without PD: censored by surgery				
Alive without PD: abandonment due to patient decision				
Total				

1: Pearson Chi-square; 2: Fisher's exact test

GEIS-30 STUDY

Statistical analysis plan

Table 51. Time to PD (weeks) (Local assessment. ITT)

	Cohort A		Cohort B		Total		p-value ¹		
	N	Mean (SD)	Median (Min-Max)	N	Mean (SD)	Median (Min-Max)		N	Mean (SD)
Time to PD (weeks)									

1: Mann-Whitney U test

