#### **10.1.2. Secondary Endpoints**

##### **Overall progression free survival (median PFS)**

Overall progression free survival will be computed from the date of start of treatment to the first documented date of progression or the date of death, whatever the cause. Patients alive and free from progression at the time of the analysis will be censored at the date of last follow-up.

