##### **Overall survival (OS)**

It will be computed from the date of start of treatment to the date of death, whatever the cause. Patients alive or lost for follow-up at the time of the analysis will be censored at the date of last follow-up.

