2.5. GLOBAL FOLLOW-UP

Table 39. Global follow-up (weeks) ITT and PP

	Cohort A			Cohort B			Total			p-value ¹
	N	Mean (SD)	Median (Min-Max)	N	Mean (SD)	Median (Min-Max)	N	Mean (SD)	Median (Min-Max)	
Global follow-up ITT										
Global follow-up PP										

1: Test Mann-Whitney

GEIS-30 STUDY

Statistical analysis plan

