2.7.3 PFS. CENTRAL ASSESSMENT. ITT

To describe the event in PFS, the protocol will be followed:

“Overall progression-free survival will be calculated from the date of initiation of treatment to the first date of documented progression or date of death, whatever the cause. Live patients with no evidence of progression at the time of analysis will be censored on the date of the last follow-up. ”

Table 56. Progression-free survival at 12 and 24 weeks according to cohorts (Central assessment. ITT)

Progression-free survival	N events	N patients at risk	% Estimated cumulative survival ratio	95% CI		
at 12 weeks	Cohort A					
	Cohort B					
at 24 weeks	Cohort A					
	Cohort B					
	Strategy	N (%) events	Median (weeks)	Min-Max	Standard error	p-value ¹
Progression-free survival	A					
	B					
	Total					

1: Log-rank test

Figure 3. Progression-free survival according to cohorts (Central assessment ITT). Kaplan-Meier curve.

GEIS-30 STUDY

Statistical analysis plan

Table 57. Progression during follow-up (Central assessment. ITT)

	Cohort A		Cohort B		Total	p-value
	N (% , 95% CI)		N (% , 95% CI)		N (% , 95% CI)	
Progression-free survival	PD					
	Alive: Free of progression					
	Total					

1: Pearson Chi-square; 2: Fisher's exact test

Table 58. Time to PD (weeks) (Central assessment. ITT)

	Cohort A			Cohort B			Total		p-value ¹
	N	Mean (SD)	Median (Min-Max)	N	Mean (SD)	Median (Min-Max)	N	Mean (SD)	
Time to PD (weeks)									

1: Mann-Whitney U test

Table 59. Follow-up time (weeks) (Central assessment. ITT)

	Cohort A			Cohort B			Total		p-value ¹
	N	Mean (SD)	Median (Min-Max)	N	Mean (SD)	Median (Min-Max)	N	Mean (SD)	
Follow-up time (weeks)									

1: Mann-WhitneyU test

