2.7.4. PFS. CENTRAL ASSESSMENT. PP

Table 60. Progression-free survival at 12 and 24 weeks according to cohorts (Central assessment. PP)

Progression-free survival	Cohort	N events	N patients at risk	% Estimated cumulative survival ratio	Standard error	95% CI	p-value ¹
at 12 weeks	Cohort A						
	Cohort B						
at 24 weeks	Cohort A						
	Cohort B						
Progression-free survival	A						
	B						
	Total						

1: Log-rank test

GEIS-30 STUDY

Statistical analysis plan

Figure 4. Progression-free survival according to cohorts (Central assessment. PP). Kaplan-Meier curve.

Table 61. Progression during follow-up (Central assessment. PP)

	Cohort A		Cohort B		Total	p-value
	N (% , 95% CI)		N (% , 95% CI)		N (% , 95% CI)	
PD						
Progression-free survival	Alive: Free of progression					
	Total					

1: Pearson Chi-square; 2: Fisher's exact test

Table 62. Time to PD (weeks) (Central assessment. PP)

	Cohort A			Cohort B			Total		p-value ¹
	N	Mean (SD)	Median (Min-Max)	N	Mean (SD)	Median (Min- Max)	N	Mean (SD)	
Time to PD (weeks)									

1: Mann-Whitney U test

GEIS-30 STUDY

Statistical analysis plan

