2.8. EFFICACY:ENDPOINT SECONDARY GLOBAL SURVIVAL (OS)

2.8.1. OS. ITT

Table 63. Overall survival at 12 and 24 weeks according to cohorts (ITT)

Overall survival	N events	N patients at risk	% Estimated cumulative survival ratio	95% CI			
at 12 weeks	Cohort A						
	Cohort B						
at 24 weeks	Cohort A						
	Cohort B						
Overall survival	Strategy	N (%) events	Median (weeks)	Min-Max	Standard error	95% CI	p-value ¹
Overall survival	A						
	B						
	Total						

1: Log-rank test

Figure 5. Overall survival according to cohorts (ITT). Kaplan-Meier curve.

Table 64. Exitus during follow-up and at 12 weeks (ITT)

	Exitus	Cohort A	Cohort B	Total	p-value
		N (%), 95% CI)	N (%), 95% CI)	N (%), 95% CI)	
Overall survival	Live				
	Loss Follow-up				
	Total				
	Reason Exitus				
Reason Exitus	No				
	Disease progression				
	Kidney failure				
	Clinical deterioration				
	Post-surgical complications				
	Unknown				
	Total Overall				
survival at 12 weeks	Exitus				
	Live				
	Total				

1: Pearson Chi-square; 2: Fisher's exact test

Table 65. Time to exit (weeks) (ITT)

	Cohort A			Cohort B			Total			p-value ¹
	N	Mean (SD)	Median (Min-Max)	N	Mean (SD)	Median (Min-Max)	N	Mean (SD)	Median (Min-Max)	

GEIS-30 STUDY

Statistical analysis plan

Exit time
(weeks)

1: Mann-Whitney U test

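### SAP Tables 51, 55, 58, 62, 65 and 68 summarise and test time to PD and time to death with no rule for censored patients, and can contradict the planned Kaplan-Meier and log-rank results

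*SAP*

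**What the plan says.** **Censoring is expected.** For PFS, protocol section 10.1.2 states: "Patients alive and free from progression at the time of the analysis will be censored at the date of last follow-up". For OS: "Patients alive or lost for follow-up at the time of the analysis will be censored at the date of last follow-up". SAP section 2.7.3 repeats the PFS rule. SAP Table 50 has rows for patients alive without PD at the end of follow-up, after surgery, or after leaving by their own decision. Tables 64 and 67 have rows for patients alive and lost to follow-up.

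**The main analysis handles it.** Protocol section 10.4 specifies Kaplan-Meier estimation of PFS and OS in each stratum. SAP Tables 48, 52, 56 and 60 (PFS) and 63 and 66 (OS) give estimates at 12 and 24 weeks, overall summaries by cohort and log-rank tests, with Kaplan-Meier curves.

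**The same sections add a second set.** "Table 51. Time to PD (weeks) (Local assessment. ITT"), "Table 62. Time to PD (weeks) (Central assessment. PP") and "Table 65. Time to exit (weeks) (ITT"), with Tables 55, 58 and 68, give N, mean (SD), median (min-max) and a p-value footnoted "1: Mann-Whitney U test" or a close variant. None defines N or says how a patient without the event is treated.

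**The concern.** The column N can be read in two ways, and neither handles censoring. If N is the patients with the event, those who did best are left out. If N is everyone, a censored time is counted as an event time. Because the SAP does not choose, the choice could be made after the data are seen.

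Median PFS and OS are named secondary objectives. The report would carry a second median and a second cohort p-value beside each Kaplan-Meier result, and nothing says which governs. A reader could take the shorter median as the result, or take a Mann-Whitney p-value as evidence for or against a difference between histologies.

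**Working it through.** The plan states no figure for these tables, so there is none to reproduce. The question is how far the naive summaries depart from the truth.

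**Inputs from the documents**
- 30 months of accrual and 12 months of follow-up (protocol 1.18, SAP 1.15): 12 to 42 months per patient, about 52 to 182 weeks.
- SAP end date of 2 March 2018, about 33 months after a last entry in the second quarter of 2015: 33 to 63 months, about 143 to 273 weeks.
- Background medians (protocol 4.1): OS 15 months (65 weeks) and PFS 3.6 months (15.65 weeks) in a WD/DD series; OS about 8 months (35 weeks) after second line.
- Success rate of 40% at 12 weeks (protocol 10.4): exponential median 12·ln 2/(−ln 0.4) = 9.08 weeks.
- 37 patients per cohort, or 17 if stopped at stage 1.

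**Assumptions:** exponential times and uniform accrual; dropout, which the documents do not give, of 0 to 30% by week 12.

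**Formulas.** Let λ = ln 2/median and let follow-up be uniform on (a, b).
- Proportion censored: c = (e^(−λa) − e^(−λb)) / (λ(b − a)).
- Events-only median, when it falls before a: t = −ln(1 − 0.5(1 − c))/λ.
- Censored times counted as events: the t that solves e^(−λt)·P(C > t) = 0.5, where C is the follow-up time.

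**OS, median 65 weeks, follow-up 52–182 weeks.** λ = 0.01066.
- c = (0.574 − 0.144)/1.386 = 0.31.
- Events only: −ln(1 − 0.345)/0.01066 = 39.6 weeks.
- All as events: at 59.5 weeks, 0.530 × (182 − 59.5)/130 = 0.50, so 59.5 weeks.

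**OS, median 65 weeks, follow-up 143–273 weeks.**
- c = (0.218 − 0.054)/1.386 = 0.12.
- Events only: −ln(1 − 0.441)/0.01066 = 54.6 weeks.
- All as events: 65 weeks, since all censoring falls after the median.

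**Time to PD, median 15.65 weeks, follow-up 52–182 weeks, no dropout.** c = 1.7%; naive medians 15.3 (events only) and 15.6 (all as events).

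**Time to PD with dropout hazard θ.** Ignoring administrative censoring, both naive medians equal ln 2/(λ + θ). Dropout of 10% by week 12 gives θ = −ln(0.9)/12 = 0.0088; 20% gives 0.0186.
- True 9.08 weeks becomes 8.1 or 7.3.
- True 15.65 weeks becomes about 13.1 or 11.0.

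**Tests, by simulation at two-sided 5%**

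| Setting | Mann-Whitney, events only | Mann-Whitney, all as events | Log-rank |
|---|---|---|---|
| Power, OS 65 v 35 weeks, 37 v 37, equal follow-up 52–182 weeks | 19% | 55% | 66% |
| Type I error, OS, equal follow-up | 5.0% | 4.6% | 4.9% |
| Type I error, OS, 37 v a cohort stopped at 17 with follow-up of 28–42 months | 8.7% | 9.5% | 5.2% |
| Type I error, OS, follow-up 12–27 v 27–42 months | 30.1% | 24.6% | 5.3% |
| Type I error, PFS median 9.08 weeks, dropout 10% v 30% | 9.9% | 12.4% | 5.6% |

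Kaplan-Meier recovered the true median in the scenarios simulated (for example 65.3 against 65.2 weeks).

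**The case against.** The strongest defence is that the endpoint analyses are already right. The six tables are titled time to PD and time to exit, not PFS or OS, and may be meant only to describe patients who had the event. Cohorts are analysed separately, comparing them is not an objective, and no decision rule uses these tables. All of that stands and limits the weight of the point. It does not remove it: an events-only description needs that label, and a cohort p-value on it serves no stated purpose.

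A reader might also infer more than the documents support:
- *That the reported PFS and OS are biased.* They are not; the planned Kaplan-Meier and log-rank results are unaffected.
- *That the naive medians are always too short.* Bias in time to PD is negligible without dropout, and the OS median is unbiased if everyone is counted and all censoring falls after it.
- *That the Mann-Whitney p-values are invalid as such.* With equal censoring, type I error stays near 5%. It rises only if censoring differs, which is plausible because cohorts recruit independently and one may stop at 17, but is not established. Very large inflation needs a follow-up gap that nothing in the documents supports. With follow-up to the SAP's end date, even placing one cohort wholly in the early half of accrual and the other wholly in the late half gives only 9% (events only) or 5% (all counted).
- *That "Table 39. Global follow-up (weeks) ITT and PP" and "Table 59. Follow-up time (weeks) (Central assessment. ITT") make the same error.* Observed follow-up is fully observed. Those tables leave the quantity undefined, and deaths shorten it, but that is not mishandled censoring.

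**Conclusion.** The point holds as a minor-to-moderate correction. As written, the six tables ignore censoring that the protocol and SAP both expect, and can contradict the sound analyses beside them.

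The size depends mainly on OS follow-up. At a true median of 65 weeks, the understatement is about 25 weeks (events only) or 6 weeks (all as events) under the planned minimum follow-up, and about 10 weeks or none under follow-up to March 2018. The loss of power needs no imbalance in censoring. Inflated type I error does.

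These sizes rest on exponential survival, uniform accrual and background medians taken from other series. Material bias in time to PD rests on dropout rates that the documents do not give.

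**What to change.** - Delete Tables 51, 55, 58, 62, 65 and 68. Alternatively, keep them, label them *patients with the event only, descriptive*, and remove the Mann-Whitney p-values.
- State in SAP sections 2.7 and 2.8 that the Kaplan-Meier medians and log-rank tests in Tables 48, 52, 56, 60, 63 and 66 are the PFS and OS results.
- Optional good practice: define follow-up in Tables 39 and 59 and report its median by reverse Kaplan-Meier.

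The cost is SAP wording and fewer tables or p-values; no new data are needed. This does not settle the growth modulation index. SAP section 2.9 uses each patient's time to PD as the numerator and gives no rule for patients without PD, so that rule must be written separately.
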